
Schedule of activities

After a single visit screening process, eligible subjects will be enrolled in this study for 12 months each. They will visit the HNRCA as follows: 1) enrollment visit - sign consent form, receive oral D₃-creatine dose, and have practice leg endurance measurement; 2) baseline visit – medical history and physical measures, DXA scans, blood draw, pill dispensing and receive first drug dose, and have pre-dose, 1-hr post first dose, and 4-hr post first dose ECGs (ECGs this visit only); 3) 2 mo visit – repeat baseline measures (except D₃-creatine), pill count; 4) 6 mo visit – repeat baseline measures (except D₃-creatine), pill count; 5) 3 days prior to final 12 mo visit – receive oral D₃-creatine dose; 6) 12 mo visit – repeat baseline measures and pill count. Additionally, subjects will be called at 4, 8, and 10 mo to reinforce pill compliance and to answer any questions they may have.

INTRODUCTION

Rationale This study is an initial evaluation of the effectiveness of the novel ghrelin receptor agonist, anamorelin, on increasing muscle mass, strength, and function and enhancing bone formation in men and postmenopausal women with low bone and muscle mass (osteosarcopenia, OS). Anamorelin has been tested in normal adults and in patients with cancer cachexia but it has not been tested in patients with osteopenia, sarcopenia, or OS.

Background Osteopenia and sarcopenia result from the age-related losses of bone and muscle mass that occur at about 1-2% per year after age 50 years (1-3). Muscle strength declines more rapidly than muscle mass (4-6), nonetheless the loss of muscle mass is a major factor in the decline in strength that occurs with aging (7-10). The definition of osteopenia is standardized, and refers to a BMD T-score of -1 to -2.5. Currently there is no standardized definition of sarcopenia. Mounting recent evidence indicates that lower levels of functional measures, grip strength and gait speed, are significant predictors of falls and hospitalizations,

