ECGs before and 1 & 4 hr post dose		X					^e DXA total body scans at 2, 6, &12 mo; spine and non-dominant hip scans at 12 mo (screening scans will serve as baseline)
Diet assessment ^a		X				X	^f Serum P1NP at 0, 2, 6, and 12 mo; serum IGF-1 and CTX at 0 and 12 mo; serum 25(OH)D at 0 and mo 6; and alpha-acid glycoprotein at visit 0; archive 4 aliquots serum and 1 of plasma at 0 and 12 mo.
Questionnaires ^b		X		X		X	^g Safety monitoring: fasting plasma glucose & serum AST/ALT at 0, 2, 6, and 12 mo; symptoms and other AEs documented
Muscle strength ^c	X	X	X	X		X	^h By pill diary and counting returned pills
Muscle perform. ^d		X	X	X		X	ⁱ Administer 60-mg oral dose of D ₃ -creatine
DXA scans ^e			X	X		X	^j Collect fasting spot urine for D ₃ -creatine dilution determination
Study blood ^f		X	X	X		X	
Dispense pills		X	X	X			
Safety measures ^g		X	X	X		X	
Adherence ^h			X	X		X	
D ₃ -creatine dosing ⁱ	X				X		
Fasting spot urine ^j		X				X	
Waist circumference						X	

In addition to the above study visits, we will contact participants by telephone at 4, 8, and 10 months to determine whether they have any study related concerns and to remind them of the importance of taking one study pill per day. The content of these calls will be documented on the Call/comment Log.

C. Inclusion and exclusion criteria

Inclusion criteria: Ability to sign informed consent form; community dwelling men (who are sterile or agree to use contraception throughout the study) and postmenopausal women (no menses for 5 years; early postmenopausal women are ineligible because their bone turnover rate is changing rapidly); age 50 years and older; sarcopenia defined as maximum grip strength <35.5 kg (men) and <20 kg (women) in either hand (excluding hands with severe pain or recent surgery) and/or gait speed <0.8 m/sec (11); osteopenia defined as spine (at L1, L2, L3, or L4) or non-dominant total hip or femoral neck BMD T-score between -1.0 and -2.5; mini-mental state examination (MMSE) score >21.

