Pharmacy requires written orders before dispensing. The orders will contain the Protocol name, IRB #, PI name, subject name, DOB, Allergies, Subject ID, visit #; in addition to the prescription and directions and number of tablets to be dispensed (70 pills at baseline, 130 pills at 2 mo, and 190 pills at 6 mo.; note that each dispensing will contain 7-9 extra pills to cover any needs for rescheduling). Each dispensing of capsules will contain an outer label and an inner label. The outer label will be retained by Pharmacy.

Outer label content: Rx # assigned by Pharmacy; PI's Name; Subject name and ID; Date dispensed; Expiration date; either ANAMORELIN 100 MG or PLACEBO; quantity (either 70, 130, or 190).

Inner label content: Rx # assigned by Pharmacy; PI's Name; Subject name and ID; Directions: take one pill by mouth each morning at least 1 hour before breakfast; Date dispensed; Expiration date; "1 ANAMORELIN 100 MG/PLACEBO tablet"; quantity (either 70, 130, or 190); and sticker indicating "For investigational use only".

Drug disposition at end of study: The TMC Pharmacy will destroy any unused pills. They will notify Helsinn Therapeutics when this has been done.

F. Measurement procedures

Baseline and follow-up medical history

On the baseline (month 0) visit, subjects will be asked questions about their medical history and demographics including race, ethnicity, education level, and marital status (see baseline medical history and Demographics forms). The follow-up medical histories taken on each subsequent visit focus on recent medical history and medication use (see follow-up medical history form).

Performance and strength measurements

HABC-PPB - The short physical performance battery (SPPB) captures domains of lower extremity strength, endurance, and balance; it is highly predictive of subsequent disability (34). To broaden the applicability, the Health ABC investigators expanded the SPPB by increasing the duration of balance stands (to 30 seconds), adding a single foot stand, and adding a 6-meter narrow walk test of balance (35). They also adapted the scoring method to reduce the ceiling effects that are common in moderate to well-functioning groups. In Health ABC, the 3-year decline in lower-extremity performance assessed by the HABC-PB was consistent with clinically meaningful declines in usual gait speed and walking endurance (35).

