DXA scans will be performed by DXA technicians who are experienced and certified by International Society for Clinical Densitometry and the State of MA. Should a participant's BMD of the spine or hip decline by >7% on 2 consecutive measurements, the participant will be notified and referred to his/her PCP. The participant will remain in the study.

The muscle performance measurements will be administered by an experienced research coordinator who will observe the subject during testing.

Because of the potential of anamorelin to increase fasting plasma glucose, we will monitor glucose on each visit. If it is elevated (≥ 200 mg/dl), we will repeat the measurement. If again elevated ≥ 200 mg/dl, the study pills will be discontinued. Discontinuation of study pills will be managed without unblinding the study team, and those participants will continue with study measurements (for the intent-to-treat analysis). Subjects will be asked to consume their usual dinner on the evening prior to each study visit.

Sporadic, mild increases in serum AST/ALT have been observed in subjects on anamorelin. We will monitor AST/ALT on each study visit and discontinue use of anamorelin if these levels exceed 2x the upper end of the reference range (>74 and >68 MU/ml, respectively) on repeat measurement.

In order for participants to achieve therapeutic levels of anamorelin, we will exclude subjects on CYP3A4 inducers which may increase the metabolism of anamorelin (e.g., rifampin). We will also have participants take study pills 1 hour before breakfast, as food reduces anamorelin bioavailability.

To minimize risk that anamorelin levels become supra-therapeutic, we will: a) instruct participants never to take more than one study pill per day (that is, not to 'catch up' after missing a dose); b) exclude participants taking strong CYP3A4 inhibitors (ketoconazole, clarithromycin, itraconazole, nefazodone, telithromycin); c) exclude participants taking drugs with high binding affinity to AAG because they have the potential to displace anamorelin from binding (e.g., carvedilol, chlorpromazine); d) exclude participants taking inhibitors of P-glycoprotein (e.g., verapamil, quinidine), and e) inhibitors of OATP1B3 (e.g., cyclosporine, rifampicin)

We will instruct participants to notify [name] of any new prescriptions (before taking the first dose) and of any changes in health status or of any hospitalizations or emergency room visits.

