Nonclinical data indicate that the T_{max} in cardiac tissue is delayed compared with plasma T_{max} (4 hrs vs 1 hr, respectively). We will perform a screening ECG and exclude individuals with clinically meaningful abnormalities. We will also perform ECGs before and 1 and 4 hrs after the first dose of the study pills.

Stopping rules

- We will discontinue the subject's participation in the study if the QT interval exceeds 470 ms or if other clinically meaningful ECG changes occur at either 1 hr or 4-hrs post first dose (4 hrs post dose is the time when the anamorelin concentration in cardiac tissue is maximal).
- We will discontinue the subject's participation in the study in the event that he/she develops cardiac symptoms (e.g., chest pain, chest pressure, palpitations) or evidence of significant fluid retention (peripheral edema, pulmonary congestion).
- We will discontinue a subject's participation in the study if he/she is prescribed the following drugs during the study:
 - CYP3A4 inhibitor (ketoconazole, clarithromycin, itraconazole, nefazodone, or telithromycin)
 - Channel blocking antiarrhythmic medication (flecainide, procainamide, propafenone, quinidine)
 - Drugs with high affinity to AAG (carvedilol, chlorpromazine)
 - Inhibitors of P-glycoprotein (verapamil, quinidine)
 - Inhibitors of OATP1B3 (cyclosporine, rifampicin)
- We will discontinue a subject's participation in the study if he/she develops glycemia defined as fasting plasma glucose ≥ 200 mg/dl on two consecutive measures.

Subjects developing these findings or symptoms will be referred to their physicians and these adverse events will be recorded and reported to the IRB, the NIH, and Helsinn Therapeutics. The study physician will follow up with the subject and his/her physician until symptoms have been appropriately addressed.

We will exclude subjects with eGFR < 30 ml/min.

The study will be approved by the Tufts IRB before anyone will be recruited for the study. All study personnel have been certified by the Tufts IRB to work with clinical research participants. All research activity will take place at the HNRCA. Written informed consent will be obtained from each participant.

The PI will inform the IRB of any updated information that may affect the conduct of this study or subject safety, rights, welfare or willingness to take part in the research.

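### The calls at 4, 8 and 10 months specify no question on new drugs, symptoms or adverse events, so structured enquiry lapses for up to 6 months and detection of symptom- and drug-based stopping events relies on what participants volunteer

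*Combined protocol and SAP*

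**What the plan says.** **Calls.** The opening Schedule of activities says that "subjects will be called at 4, 8, and 10 mo to reinforce pill compliance and to answer any questions they may have". Research Design, section B describes the same calls as made "to determine whether they have any study related concerns and to remind them of the importance of taking one study pill per day". It adds: "The content of these calls will be documented on the Call/comment Log". No adverse event or medication form is named for them.

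**Visits.** Footnote g to the section B table, attached to the safety row, lists "fasting plasma glucose & serum AST/ALT at 0, 2, 6, and 12 mo; symptoms and other AEs documented". Section F (Baseline and follow-up medical history) says: "The follow-up medical histories taken on each subsequent visit focus on recent medical history and medication use". After baseline, the visits fall at 2, 6 and 12 months.

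**Self-report.** Under Protection against risks, participants are told to notify the study "of any new prescriptions (before taking the first dose) and of any changes in health status". Hospitalizations and emergency room visits are covered by the same instruction.

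**Stops.** Stopping rules ends participation for cardiac symptoms or significant fluid retention, and also "if he/she is prescribed the following drugs during the study", followed by a list of interacting drugs. The same section has a rule for ECG changes 1 and 4 hours after the first dose and a rule for repeated high fasting glucose. Protection against risks has a further rule for AST/ALT.

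**The concern.** A cardiac symptom, oedema or a new prescription can arise on any day of the 12 months. Three contacts are already placed between the visits, yet as described they promote daily dosing without first checking for the events that would end it. A participant who does not connect ankle swelling, or another doctor's prescription, with the study may not raise it when asked about concerns, and would then be reminded to take the pill.

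Three features of the plan give this some weight:

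- In-study ECGs are confined to the baseline visit, around the first dose. After that, cardiac safety rests on symptom and drug enquiry.
- The anamorelin safety experience cited in the Background runs to 6 months of treatment. The longest interval without structured enquiry, months 6 to 12, lies beyond it.
- Aim 2C describes safety and tolerability, and section J bases this partly on clinical symptoms. Expedited reporting of serious events runs from when the investigator becomes aware, and the report needs an onset date. Section J also excludes participants who start glucocorticoids or an osteoporosis drug from the per-protocol analysis, so medication dates matter there too.

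**Working it through.** No power or alpha calculation applies. The check is interval arithmetic plus a comparison of what each contact is stated to cover.

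**1. Confirm the visit intervals from the dispensing counts (section E).** The plan dispenses 70, 130 and 190 pills at 0, 2 and 6 months and says each supply holds 7 to 9 extra. With one pill a day and 365.25/12 = 30.4375 days per month:

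| Interval | Days | Pills | Extra |
|---|---|---|---|
| 0–2 months | 2 × 30.4375 = 60.9 | 70 | 9.1 |
| 2–6 months | 4 × 30.4375 = 121.8 | 130 | 8.2 |
| 6–12 months | 6 × 30.4375 = 182.6 | 190 | 7.4 |

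The plan's figure is reproduced, so the 6-month final interval is as intended.

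**2. Intervals between structured enquiries.**

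- Visits only (0, 2, 6, 12): 2, 4 and 6 months. The longest is 6.
- Visits plus calls (0, 2, 4, 6, 8, 10, 12): 2 months throughout. The longest is 2.

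**3. What the worst case means on average.** Assume, for illustration only, that an event is equally likely at any time in the 12 months and is never volunteered. The mean wait to the next structured enquiry is the sum of squared intervals divided by twice their total.

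- Visits only: (2² + 4² + 6²) / (2 × 12) = 56/24 = 2.3 months.
- With the calls: (6 × 2²) / (2 × 12) = 24/24 = 1 month.

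Both are upper figures, because some participants will report sooner.

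**4. Contacts used.** 3 calls × 32 enrolled = 96 at most. For the 24 expected completers alone it is 3 × 24 = 72.

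**5. Which stops a call could detect.**

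| Rule | Detectable by telephone? |
|---|---|
| Cardiac symptoms, fluid retention | Yes, by asking |
| Listed drug prescribed | Yes, by asking |
| ECG change at 1 or 4 hours after first dose | No; completed at the baseline visit |
| Fasting glucose, AST/ALT | No; these need laboratory values, and their longest interval stays 6 months |

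**The case against.** The strongest reply is that the plan already has a faster safeguard than any call. Participants are told to report every new prescription before its first dose, so they need not recognise an interacting drug; the study team does that check. If the instruction is followed, a listed drug is caught before any combined exposure, which a call at month 4, 8 or 10 cannot guarantee. Participants must also score above 21 on the MMSE and show that they understand the procedures. This stands, and it rules out any suggestion that stopping events have no reporting route between visits. What remains is that the route depends on the participant acting first, and no contact between visits confirms that it was used.

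A reader might infer that the calls ask nothing, or that anyone meeting any stopping rule can go unasked for six months. The documents do not support this. The calls openly ask about concerns and the content is logged, so symptoms may well come out. Only the symptom and listed-drug rules could be picked up by telephone.

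Adverse events are defined without regard to how they come to light, so a problem raised on a call can be recorded as one. That also stands. The gap is in asking, and in naming where the answer is recorded.

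Finally, the Call/comment Log and the follow-up history form are not in the documents and may already contain such questions. This cannot be checked. If they do, a sentence in section B settles the matter.

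**Conclusion.** The point holds in a limited form. Between the 2, 6 and 12 month visits, detection of the symptom-based and listed-drug stopping events depends on volunteered information. The longest interval without structured enquiry is 6 months, and it could be about 2 months using contacts already planned.

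This is a weakness of design, not a contradiction: open self-report, open calls and structured visits are compatible with one another. The conclusion assumes that visits and calls take place at their nominal times and that no unseen call script already asks these questions.

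Two stronger inferences are not supported. The documents do not show that any stopping event would be missed. They also give no rate of listed-drug prescriptions or between-visit symptoms, so neither the number of events found earlier nor the size of any under-count of mild events can be stated. Ascertainment is scheduled identically in both blinded arms, so the point concerns the timing and completeness of safety data and not a demonstrated bias between arms. It is worth making as a cheap improvement.

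**What to change.** Amend the call content in both places where it appears: the opening Schedule of activities and Research Design, section B. Before the pill reminder, each call asks a short fixed set of questions covering the time since last contact:

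- new or changed medications, which staff check against the protocol's drug lists;
- symptoms, including those named under Stopping rules;
- hospital or emergency visits.

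Record the answers as adverse event and medication data with onset dates, as well as on the Call/comment Log. Positive answers go to the study physician and are handled under the rules already in the protocol. No new clinical rule is proposed, and the laboratory and ECG schedules are untouched. If a call script already covers this, cite it in section B.

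The cost is a small protocol and form amendment and a few extra minutes on each of at most 96 calls, with no added visit or test. Slightly more adverse events will be recorded, in both arms alike.

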The Bioinformatics Specialist, [name], will create the one to one randomization allocation for this study using a block randomization stratified by sex. Due to the small sample size, a block size of 4 will be used. At enrollment, subjects will be randomized by a research coordinator using the randomization module in REDCap. When the subject comes for the baseline visit, a research coordinator will notify the TMC pharmacy of the treatment assignment (group A or group B). A research coordinator will pick up the pill bottle from the Pharmacy and give it to the subject. With the exception of the bioinformatics specialist, the study statistician,

and the pharmacist, all study personnel will be blinded to treatment assignment. In the event of an SAE and upon recommendation of the study physician, the bioinformatics specialist will inform the participant's primary care physician of the treatment assignment. The study physician will remain blinded.

H. Data management

Data collected during this single-site study will not leave the site. All data will be entered into electronic data capture (EDC) forms built in REDCap. Primary data records include: EDC forms completed by the research coordinator during subject interviews and physical measurements, electronic database files generated directly by the DXA bone scanning equipment, and electronic database files of biochemical screening tests generated by the Nutrition Evaluation Laboratory.

All electronic data forms will utilize data entry validation for data types and data ranges to minimize potential for error and will undergo monthly data quality checks by a member of the Biostatistics and Data Management Core Unit at the HNRCA to ensure data quality.

The study database and all source data will be maintained on the HNRCA REDCap server for a minimum of 10 years post study completion per the HNRCA data retention policy. Duplicate copies of these data will be maintained on the HNRCA disaster recovery server as well as the Bone Metabolism Laboratory network storage.

Electronic DXA data files are generated by the DXA scanner located in the Bone Metabolism Laboratory. Biochemical data are manually entered by staff of the Nutrition Evaluation Laboratory and transferred into REDCap. Original paper copies of biochemical assay results are kept in the Nutrition Evaluation Laboratory until and beyond the end of all study activity.

I. Study power

Aim 1: Muscle mass by D₃-creatine dilution –

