The recently published study in Duchowny et al. (13), looked at change in muscle mass assessed by the D₃-creatine dilution method. Table 2 in the paper reports estimated mean change in D₃-Cr muscle mass over 1.6 years in 40 men (mean age 83 years), duplicated below.

Table Simple linear change

variable	mean	SD
D ₃ -Cr muscle mass (kg)	-1.42	1.84
weight (kg)	-0.63	2.92
D ₃ -Cr muscle mass/weight	-0.02	0.02

We will use SD=1.84 to represent standard deviation of change for D₃-Cr muscle mass (kg). Additionally, -1.42 kg over 1.6 years is equivalent to -0.89 kg per year (what we might expect in the placebo group).

A difference (anamorelin vs placebo) in 3 month change of 0.57 kg and 0.83 kg in appendicular LBM was observed in the two replicate studies (26). Assuming a linear rate of change, we can expect a change in muscle mass of 2.28-3.32 in 12 months. A linear rate of change is reasonable since in the safety extension of these original trials, continued response in weight change during the trial was observed out to 6 months (29).

Twelve participants per group are required to have a minimal detectable difference below 2.28 kg between anamorelin and placebo.

Aim 2: P1NP- The bone formation marker, P1NP, is the key secondary endpoint. Between-subject variation in 84-day change in P1NP was estimated from our previous clinical trial in 244 men and women age 50 and older (42). Standard deviation of 84-day change in P1NP was 0.267 nmol/L in all three treatment groups (42). With N=12 completers per group, statistical power is 82% to detect a difference of 0.32 nmol/L between placebo

and treatment, which is a 25% change. P1NP has not been measured in anamorelin treated subjects, but detecting a 25% group difference from placebo is clinically meaningful and it is plausible given that another ghrelin receptor agonist, MK-677, induced a 29% increase in another bone formation marker, serum osteocalcin, over a 2-week period (30).

J. Data analysis

Baseline subject characteristics will be tabulated and summary statistics reported for all measured outcomes at each time point.

Primary aim – The change in muscle mass over 12 months will be compared between the intervention and control groups with a two-sample Student's t-test. Should the groups be imbalanced in factors known to influence muscle mass (i.e., sex, age, HABC-PPB, physical activity level, and dietary protein intake), we will adjust for those confounders within an ANCOVA model.

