Secondary aims - With 4 measurements (baseline, 2, 6, and 12 months), we will test whether the change over time is linear with use of linear models with random effects. The observed pattern of change in ALM over time will give an indication of the potential long-term benefit (or lack thereof) of anamorelin treatment. A significance level of 0.05 will be used.

The findings from secondary (and exploratory) analyses will be used for hypothesis generation, rather than to draw conclusions.

Exploratory aims – Exploratory outcomes will be analyzed as described above. For those with more than two measurements, the pattern of change will be analyzed as described above for ALM.

The primary analyses will follow intention-to-treat principles. The intent to treat population will include all subjects who had 1 or more visits after visit 0 (baseline). We will also perform per protocol analyses, in which subjects who develop clinical conditions during the study that influence the study outcomes (i.e., started treatment on an osteoporosis drug or glucocorticoids) or with selected protocol deviations will be excluded. Data will be diagnosed to evaluate validity of model assumptions. Assumptions of normality and homoscedasticity will be evaluated in these models and appropriate variable transformations will be applied if needed to satisfy model assumptions. If model assumptions do not hold for the linear mixed models, robust standard errors will be used. An exploratory per-protocol analysis will also be performed.

Safety and tolerability measures will be summarized for each treatment group based on clinical symptoms and circulating levels of glucose and ALT/AST. Adherence will be assessed by intake diary and pill counts.

K. Withdrawal from the study

Participants can go permanently “off study” only for withdrawal of consent, defined as no longer wishing to participate in all aspects of the trial. The PI may also withdraw participants for safety reasons. Participants can be off of study pills (non-adherent) but remain in the study and return for scheduled follow-up visits. Participants who are instructed by their doctor to gain weight during the study will not be withdrawn from the study.

PROTECTION OF HUMAN SUBJECTS

a. Materials and potential risks

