Statement of compliance: The trial will be conducted in compliance with the protocol, International Council for Harmonization/Good Clinical Practice requirements (ICH/GCP), and applicable state, local and federal regulatory requirements.

Data and Safety Monitoring: The PI will ensure that each candidate meets eligibility criteria before enrollment, will closely monitor all study activities, will review and classify all adverse events, ensure that adverse events are reported in the appropriate time lines to the IRB, prepare annual IRB recertification documents. The NIH will appoint a Safety Officer who will oversee the conduct of the study. The PI will provide reports to the Safety Officer and to the NIH, with the content requested and at the requested intervals.

To ensure confidentiality of subject information: Personal information of subjects who consent to participate in the study will not be given to anyone unless the law requires it. Every effort will be made to keep subjects' information private, but this cannot be totally guaranteed. The Tufts Medical Center Institutional Review Board (IRB) or the HNRCA may check records that identify subjects. These records may include medical or research records and the signed informed consent form, which will be kept in a locked medical records room in the HNRCA Volunteer Services department. Only authorized personnel may access the record. The HNRCA Volunteer Services department is staffed during normal work hours and is locked during non-working hours. If it is necessary for a medical record to leave the admissions office, it must be signed out only by an HNRCA employee (who is identified by Tufts ID) in a log of the HNRCA ID, name of employee taking possession of the chart, and the date. The records of this study might also be reviewed to make sure all rules and guidelines were followed.

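### The study statistician is listed as unblinded with no reason or end date, while covariate adjustment, transformation and per-protocol exclusions are not fixed before the codes are seen

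*Combined protocol and SAP*

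**What the plan says.** **Who is unblinded.** Section G reads "With the exception of the bioinformatics specialist, the study statistician", continuing "and the pharmacist, all study personnel will be blinded to treatment assignment". No reason, time limit or firewall is given for the statistician.

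**Who holds the tasks that need the code.** The same section says the bioinformatics specialist "will create the one to one randomization allocation for this study using a block randomization stratified by sex". After a serious adverse event, "the bioinformatics specialist will inform the participant's primary care physician of the treatment assignment. The study physician will remain blinded". The pharmacist dispenses under an outer label that states the treatment (section E). For safety oversight, "The PI will provide reports to the Safety Officer and to the NIH, with the content requested and at the requested intervals" (Data and Safety Monitoring); the PI is not among the unblinded roles. No interim analysis is described.

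**What is left open in section J.**
- The primary test is a two-sample t-test on 12-month change, with a move to ANCOVA conditional on the data: "Should the groups be imbalanced in factors known to influence muscle mass". Five factors are listed and no threshold is given.
- After a check of normality and homoscedasticity, "appropriate variable transformations will be applied if needed to satisfy model assumptions". No transformation, diagnostic or cut-off is named.
- Per-protocol analyses drop participants who develop conditions that affect the outcomes (starting an osteoporosis drug or a glucocorticoid is named) "or with selected protocol deviations will be excluded". Those deviations are not listed, and nobody is named to select them.

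**The concern.** The trial is described as double-blind, but as written the blind need not cover the person who would normally fit the models. With 24 expected completers, one or two exclusions, a change of scale or a different covariate set can move a p-value across 0.05. If such choices are made by someone who knows each participant's arm and outcome, a reader cannot tell afterwards whether they were driven by the data's structure or by the answer.

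The three choices differ in reach. The conditional ANCOVA matters most because it bears directly on the primary comparison. The transformation rule, as worded, can also reach it. The per-protocol exclusions cannot change the intention-to-treat result; they affect only how far the exploratory analysis can be trusted.

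**Working it through.** **Step 1. Does any described task require the statistician to hold the codes?**
- Creating the allocation: bioinformatics specialist (G).
- Disclosure after a serious adverse event: bioinformatics specialist (G).
- Dispensing: pharmacist (E, G).
- Reports to the Safety Officer: PI, who is blinded (Data and Safety Monitoring).
- Interim analysis: none described.

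No described task needs it. A by-arm safety table could be requested, but the bioinformatics specialist already holds the codes.

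**Step 2. The plan's own figure.** Section I (Study power) gives SD 1.84 kg and 12 per group for a detectable difference below 2.28 kg. Assume two-sided alpha 0.05 and 80% power, since power is not stated for this aim. The normal approximation at n = 12 is (1.960 + 0.842) × 1.84 × √(2/12) = 2.10 kg. With the noncentral t, the detectable difference is 2.20 kg at n = 12 and 2.31 kg at n = 11, so 12 is the smallest n below 2.28 kg. The stated figure reproduces and is not in dispute.

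**Step 3. Latitude in the per-protocol analysis.** Simulate no true effect, 12 per arm, SD 1.84 kg, two-sided t-test at 0.05. Let k participants have some deviation. Compute t = (mean₁ − mean₀) / [s_pooled √(1/n₁ + 1/n₀)] for each of the 2^k possible exclusion sets, and count a run if any set gives p<0.05 in either direction. The values of k are assumptions.

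| k | Sets (2^k) | Chance of at least one p<0.05 |
|---|---|---|
| 0 | 1 | 5.0% |
| 2 | 4 | 6.9% |
| 3 | 8 | 8.5% |
| 4 | 16 | 10.2% |
| 6 | 64 | 14.8% |

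Repeat runs agreed within about one percentage point. Two narrower readings:
- Counting only results that favour anamorelin gives 2.6%, 3.4%, 4.6%, 5.0% and 7.5% for the same k, against a nominal 2.5%.
- If exclusions go by deviation type (6 participants, 3 types of 2 each), the best of four definitions gives 9.6%. One definition fixed in advance gives 5.1%.

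**Step 4. Latitude that can reach the primary test.** These are illustrations on assumed inputs.
- Transformation: taking the better of the raw and a rank-normal scale gives 6.0%, against 5.1% for the fixed t-test in the same simulation.
- Covariates: free choice among the 2⁵ = 32 subsets of the five listed factors, taken as independent and continuous, gave 9.7% if each is uncorrelated with the outcome, 13.9% at r = 0.2 and 20.1% at r = 0.3. A repeat run gave 10.9%, 13.5% and 17.8%, so only the rough size should be used. This overstates what the plan allows: adjustment is tied to imbalance, and sex, one of the five, is a stratification factor.

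**The case against.** The strongest reply is that the primary result is largely protected. Section J names the t-test and the intention-to-treat principle, calls a per-protocol analysis exploratory, and treats secondary and exploratory findings as hypothesis-generating. The D₃-creatine laboratory is blinded to group and sample sequence (section F). Transformations are tied to model assumptions, robust standard errors are the stated fallback for the mixed models, and part of the per-protocol rule is specified. This is also a small pilot meant to guide larger studies.

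All of that stands and limits the point. It does not close the gap: the ANCOVA trigger has no threshold and the transformation rule has no stated criterion, and both can apply to the primary comparison.

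A reader might infer three stronger things that the documents do not support:
- *That the primary test has a 7% to 15% false-positive rate.* Those figures come from choosing exclusions, which the intention-to-treat test does not permit.
- *That the statistician is unblinded throughout and makes these choices.* The plan states neither. It sets no end date and names no decision-maker, so the choices could be made with the codes known.
- *That access could serve no purpose.* The Safety Officer may ask for by-arm content. That is a possible reason, but not one the plan states, and another role can meet it.

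**Conclusion.** The point holds in a limited form. The plan expressly exempts the statistician from the blind without a stated need, and it does not require adjustment, transformation or per-protocol exclusions to be fixed before codes are seen. Adjustment and transformation can affect the primary intention-to-treat result; per-protocol exclusions affect only the exploratory analysis.

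The 6.9% to 14.8% range is an upper bound for that exploratory analysis. It assumes no true effect, 12 per arm, 2 to 6 participants with deviations, unrestricted subset choice and significance in either direction. The documents give no basis for a single inflation figure for the primary test: the illustrations in step 4 rest on assumed correlations and on more freedom than the plan grants. Actual inflation depends on conduct, and no misconduct is suggested. This is a moderate weakness with a cheap remedy; it does not invalidate the primary analysis.

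**What to change.** **Section G.** Take the study statistician off the unblinded list until database lock. State that the bioinformatics specialist releases codes to the statistician only after a dated record, made blind, fixes the per-protocol exclusions by participant, the transformation rule (diagnostic, criterion and named transformation) and the model form. Masked A/B labels would not be enough, because swapping two labels leaves a two-sided p-value unchanged.

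**Section J, primary aim.** Replace the imbalance trigger with covariates named in advance, or state that there are none. Imbalance by arm cannot be judged blind, so the trigger cannot be kept alongside the change to section G.

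**Cost.** Wording changes and one blinded data-review record. Any by-arm safety table requested before lock would be produced by the bioinformatics specialist, a small shift of work to a role that already holds the codes. The planned sample size, visits and staffing do not change.
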